16.2. Publications by Investigators

Pfizer supports the exercise of academic freedom and has no objection to publication by principal investigator of the results of the study based on information collected or generated by principal investigator, whether or not the results are favorable to the Pfizer product. However, to ensure against inadvertent disclosure of confidential information or unprotected inventions, the investigator will provide Pfizer an opportunity to review any proposed publication or other type of disclosure of the results of the study (collectively, "Publication") before it is submitted or otherwise disclosed. The investigator will provide any publication to Pfizer at least 30 days before they are submitted for publication or otherwise disclosed. If any patent action is required to protect intellectual property rights, the investigator agrees to delay the disclosure for a period not to exceed an additional 60 days.

The investigator will, on request, remove any previously undisclosed confidential information before disclosure, except for any study- or Pfizer product-related information necessary to the appropriate scientific presentation or understanding of the study results.

If the study is part of a multicenter study, the investigator agrees that the first publication is to be a joint publication covering all study sites, and that any subsequent publications by the principal investigator will reference that primary publication. However, if a joint manuscript has not been submitted for publication within 12 months of completion or termination of the study at all participating sites, the investigator is free to publish separately, subject to the other requirements of this section.

For all publications relating to the study, the institution will comply with recognized ethical standards concerning publications and authorship, including Section II - "Ethical Considerations in the Conduct and Reporting of Research" of the Uniform Requirements for Manuscripts Submitted to Biomedical Journals, <http://www.icmje.org/index.html#authorship>, established by the International Committee of Medical Journal Editors.

Publication of study results is also provided for in the Clinical Study Agreement (CSA) between Pfizer and the institution. In this section entitled Publications by Investigators, the defined terms shall have the meanings given to them in the CSA.

If there is any conflict between the CSA and any Attachments to it, the terms of the CSA control. If there is any conflict between this protocol and the CSA, this protocol will control as to any issue regarding treatment of study subjects, and the CSA will control as to all other issues.

Appendix 1. Allowed and Disallowed DMARDs

Allowed DMARDs:

The following DMARDs are allowed in doses:

- Methotrexate: stable dose ≤ 25 mg/week or 20 mg/ m^2 /week for at least 4 weeks before the first dose of tofacitinib (Day 1 Visit).
- If treated with MTX, treatment must be for ≥ 3 months before the first study drug dose.

Disallowed Biologic and Non-Biologic DMARDs:

The following biologic agents and DMARDs are disallowed at any time during this study. If a subject requires (in the opinion of the investigator) treatment with one of these agents, the subject should be discontinued from the study:

- Leflunomide (Arava[®]) must have been discontinued 8 weeks prior to the first dose of study drug if no elimination procedure is followed;
- Cyclosporine, tacrolimus, sulfasalazine and azathioprine: Discontinued for 7 days prior to the first dose of study drug;
- Anakinra (Kineret[®]): Discontinued for 3 days prior to the first dose of study drug;
- Baricitinib (Olumiant[®]) and Upadacitinib (Rinvoq[®]): Discontinued for 4 weeks prior to the first dose of study drug;
- Etanercept (Enbrel[®]): Discontinued for 2 weeks prior to the first dose of study drug;
- Canakinumab (Ilaris[®]): Discontinued for 7 weeks prior to the first dose of study drug;
- Adalimumab (Humira[®]): Discontinued for 2 weeks prior to first dose of study drug;
- Infliximab (Remicade[®]): Discontinued for 3 weeks prior to the first dose of study drug;
- Golimumab (Simponi TM): Discontinued for 4 weeks prior to the first dose of study drug;
- Abatacept (Orencia[®]), Tocilizumab (Actemra[®]), Certolizumab pegol (Cimzia[®]): Discontinued for 4 weeks prior to first dose of study drug;
- Rituximab (Rituxan[®]) or other selective B lymphocyte depleting agents (either marketed or investigational): Discontinued for 1 year prior to the first dose of study drug and if CD19/20+ counts are normal by FACS analysis.

- Immunoglobulin G (IgG): Discontinued for 8 weeks prior to the first dose of study drug.

Other Disallowed Agents:

- Thalidomide (Thalidomid®), bucillamine, mizoribine, d-penicillamine, chloroquine, hydroxychloroquine, and staphylococcal protein A immuno-absorbant pheresis columns (eg, PROSORBA® device/column) must be discontinued for 4 weeks prior to first dose of study drug;
- Auranofin (oral gold), aurothioglucose (injectable gold), aurothiomalate (injectable gold) must be discontinued for 8 weeks prior to first dose of study drug.

Disallowed Investigational Drugs:

- **Investigational NSAIDs:** Any experimental non-steroidal anti-inflammatory drug (NSAID), including selective COX-2 inhibitors, must be discontinued for 4 weeks prior to the first dose of study drug;

Other Investigational Drugs: Any other experimental therapy must be discontinued for 4 weeks or 5 half-lives (whichever is longer) prior to the first dose of study drug.

Note: The above prohibited agents are permitted during the study only for subjects permanently withdrawn from Investigational Product and continuing in the study on standard-of-care in accordance with local treatment policies.

Appendix 2. Approximate Equivalent Morphine Doses of Opioid Analgesics**Common opioid analgesics**

Drug	Maximum Allowed Total Daily Dose	Relative potency to oral morphine	Half-Life
Morphine	0.2-0.5 mg/kg/dose, up to 15 mg/dose. No more than 5 doses/day.	1	1.5-4 hrs
Hydromorphone (Dilaudid)	0.03-0.08 mg/kg/dose, up to 2 mg/dose. No more than 5 doses/day.	4	2.5 hrs
Codeine (Paveral, Tylenol #2 and #3)	0.5-1.0 mg/kg/dose, up to 60 mg/dose. No more than 5 doses a day.	0.15	2.5-3.5 hrs
Oxycodone [Roxicodone; Percocet, Tylox]	0.05-0.15 mg/kg/dose, up to 5 mg/dose. No more than 5 doses a day.	~2	3.2 hrs

Sites should contact project team for acceptable alternative preparations and related data.

Lexi Comp Pediatric Dosage Handbook 15th Edition

Sick Kids Drug Handbook & Formulary 2008-2009

Rx Files Pediatric Pain: Treatment Considerations, Q & A's. Oct. 08.

Appendix 3. Permitted Adjustments in sJIA Therapies

The following adjustments of background medications are allowed for reasons of inadequate efficacy of current treatment, or may be tapered or discontinued due to disease improvement. Adjustments for safety reasons may be done at any time, but if this leads to changes in excess of those allowed below, the investigator must receive approval from the Pfizer project team to allow the subject to continue in the trial.

1. NSAIDs/COX-2 inhibitors: dose adjustments may be made, or background NSAID/COX-2 inhibitors may be switched, but should be no more frequently than every 3 months, and should be more than 14 days prior to a study visit.
2. Oral Corticosteroid (CS) dose should be stable for the duration of Part 1 of the open-label phase and not exceed 1.0 mg/kg/day up to 30 mg/day oral prednisone or equivalent daily. In Part 2 at each study visit if the subject continues to meet an adapted ACR 50 level of response, then the daily prednisone dose can be tapered in accordance with the tapering criteria of [Section 3.2](#). During the double-blind phase of the study the oral CS dose must remain stable unless the subject meets the flare criteria. At that time the subject will be discontinued from the study and the oral CS dose can be adjusted as necessary in the physician's judgment.
3. Methotrexate (MTX) may be administered either orally or parenterally MTX at doses not to exceed 25 mg/wk or 20 mg/m²/week (whichever is lower). The dose should be stable for at least 4 weeks before the first dose of investigational drug and remain stable for the duration of the study (open-label and double-blind phases).
4. Intra-articular steroids should be administered in a total dosage of no more than 2 mg/kg (up to 80 mg) of methylprednisolone or equivalent every 6 months. No more than two joints should be injected in any given 6-month period and individual joints should not be injected any more frequently than once in a 6-month period. **Injected joints will be considered active joints for the following 3 months.**

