Appendix 6. Rescue Therapy

Acetaminophen/paracetamol is allowable as rescue medication if dosed no more than 10-15 mg/kg/dose orally or 15-20 mg/kg/dose rectally (not exceeding 5 doses in 24 hours) for no more than 10 consecutive days. If a subject is already taking stable background doses of acetaminophen/paracetamol, (s)he may increase the dose up to the maximum dose stated above for up to 10 consecutive days for rescue purposes.

The following paradigm should be used to determine appropriate opioid rescue therapy:

Any of the following single opioid agents may be given as rescue medication (with or without acetaminophen/paracetamol) for no more than 10 consecutive days in the following total daily doses:

Morphine	0.2-0.5 mg/kg/dose, up to 15 mg/dose. No more than 5 doses/day.
Hydromorphone (Dilaudid)	0.03-0.08 mg/kg/dose, up to 2 mg/dose. No more than 5 doses/day.
Codeine (Paveral, Tylenol #2 and #3)	0.5-1.0 mg/kg/dose, up to 60 mg/dose. No more than 5 doses a day.
Oxycodone [Roxicodone; Percocet, Tylox]	0.05-0.15 mg/kg/dose, up to 5 mg/dose. No more than 5 doses a day.

Sustained release opioid formulations (eg, OxyContin[®], MS Contin[®]) and opioids with half-lives greater than 5 hours (eg, methadone, propoxyphene) may NOT be USED for rescue medication or increased for rescue purposes.

Intravenous or intramuscular CSs, biologic response modifiers and DMARDs other than those specified as allowed DMARDs (Appendix 1) are not allowed during this study. Intra-articular CSs be given in no more than two joints, in a cumulative dose of no more than 80 mg methylprednisolone or its equivalent in any 6-month study period. Injected joints will also be considered as having their pre-injection status (tender/painful and swollen) for the remainder of the trial.

Acetaminophen/paracetamol is not permitted as a part of combination products such as over-the-counter “cold remedies” or in combination with opioids if the acetaminophen/paracetamol dose will exceed 2.6 gm/day. Subjects who require rescue for more than 10 consecutive days should be considered for allowed JIA medication adjustments or discontinued from the trial. In addition, subjects should not be dosed with rescue acetaminophen/paracetamol or opioids during the 24 hours prior to a study visit. Baseline stable acetaminophen/paracetamol or opioids should NOT be discontinued in advance of study visits.

Subjects should not be dosed with any rescue intervention within 24 hours prior to a study visit.

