## Appendix 3. DATA DERIVATION DETAILS

### Appendix 3.1. The JIA Core Set Variables

The sJIA ACR response determination is a derived measurement utilizing each component of the JIA core set variables, which include:

- Number of joints with active arthritis;
- Number of joints with limited range of motion;
- Physician global evaluation of disease activity;
- Parent/legal guardian/subject evaluation of overall well-being (from the CHAQ);
- Functional ability (Disability Index from the CHAQ);
- ESR. For “real-time” assessment of the Adapted JIA ACR30 response during a study visit the subject’s ESR will be used to determine the percent change in inflammation biomarker.

The ACR defines a joint with active arthritis as a joint with swelling or, in the absence of swelling, limitation of motion accompanied by pain on motion, or tenderness.

See details of the calculation of functional ability (disability index from CHAQ) in [Appendix 3.9](#).

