### Appendix 3.2. The JIA Joint Counts

For swollen joints, painful/tender joints and joints with limitation of motion, respectively, before calculating the joint count, the following pre-processing step for each joint should be performed:

- If a joint receives an intra-articular injection (either at baseline or post-baseline visits), set the joint status to “Present” on or after the date of injection.
- If the site of injection is not recorded and/or cannot be identified, the joint assessment on the CRF (either “Present” or missing) will be used.

After this pre-processing, a joint assessment that is missing is considered “absent”, thus a good joint. To calculate the number of joints with active arthritis and the number of joints with limited range of motion, only “present” joints will be taken into account.

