#### **Clinical Inactive Disease:**

- No joints with active arthritis;
- No fever, rash, serositis, splenomegaly, hepatomegaly, or generalized lymphadenopathy attributable to sJIA;
- No active uveitis (as defined by the SUN Working Group);
- Normal ESR\* (within normal limits of the method used where tested) or, if elevated, not attributable to JIA;
- Physician global assessment of disease activity score of ‘best possible’ on the scale used;
- Duration of morning stiffness of  $\leq 15$  minutes;

\* The subject’s ESR result will be used for ‘real-time’ assessment. The normal range of ESR is 0 – 20 mm/hr.

If any of the components is missing, the components that are not missing will be used to determine the Clinical Inactive Disease Status as follows:

- Inactive disease: all components must be present (non-missing) and meet all conditions.
- Active disease: at least one component is present (non-missing) and does not meet the condition.
- Not determined: any other scenarios.

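### Protocol Appendix 3, Protocol Appendix 6 and SAP Appendix 3.2 score an injected joint by conflicting rules, so real-time remission and programmed remission can disagree for the same child

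*Protocol*

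**What the plan says.** Three places state how a joint is scored after an intra-articular steroid injection.

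- Protocol Appendix 3: "Injected joints will be considered active joints for the following 3 months".
- Protocol Appendix 6: "Injected joints will also be considered as having their pre-injection status (tender/painful and swollen) for the remainder of the trial".
- SAP Appendix 3.2, applied separately to swelling, pain/tenderness and limitation of motion: "If a joint receives an intra-articular injection (either at baseline or post-baseline visits), set the joint status to" (the value assigned is Present). The setting takes effect "on or after the date of injection". No end date is given and pre-injection status plays no part. There is one fallback: "If the site of injection is not recorded and/or cannot be identified", the CRF joint assessment is used.

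Injections are allowed on study: "No more than two joints should be injected in any given 6-month period" (Protocol Appendix 3).

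The scoring feeds remission as follows.

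- SAP Appendix 3.1: "The ACR defines a joint with active arthritis as a joint with swelling", so swelling alone makes a joint active.
- SAP Appendix 3.7 and Protocol Section 8.1.9 require, for inactive disease, "No joints with active arthritis".
- After 24 consecutive weeks of inactive disease in the double-blind phase the child leaves the study as a completer (Protocol Section 3.3) and is censored in the primary estimand (SAP Section 2.3.1).
- The coordinating center confirms inactive disease in real time (Protocol Sections 3.1 and 8.1.12).
- For analysis, the sponsor programs every efficacy endpoint except double-blind flare (SAP Sections 5.2 and 7.1) and derives remission from programmed inactive disease (SAP Section 5.3.2.3).

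**The concern.** Two of the rules sit in one protocol and cannot both be followed. The third is in the SAP and matches neither exactly. Inactive disease is judged twice, by the center during the trial and by the sponsor's program afterwards, so a difference in the joint rule becomes a difference in the endpoint. A child whose injected joint is quiet at every later examination could end participation as a remission and be censored in the primary analysis, yet appear as active disease in the secondary analyses of inactive disease and remission.

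The rule also enters the derived active-joint and limited-motion counts, the adapted ACR responses and JADAS-27. The clinical study report could then show a remission completer in the disposition table whom the endpoint table does not count as a remission.

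**Working it through.** The documents give no figure to reproduce here. The check is a timeline for one child under each rule.

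**Inputs**
- Double-blind visits every 4 weeks (Protocol Section 6.7).
- 24 consecutive weeks of inactive disease, counted from double-blind Day 1 (SAP Section 5.3.2.3).
- Assumed: one injected joint, active before injection and quiet at every examination afterwards; all other criteria met; injection site recorded.
- Assumed: 3 months is 12 weeks (84 days) or 91 days. The protocol does not define it.

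**Formula.** For an injection at double-blind week t ≥ 0, earliest remission visit = t + D + 24, where D is the number of weeks to the first visit at which the joint is no longer scored active.

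- Appendix 3, 3 months = 84 days: the visit 12 weeks later (12 × 7 = 84) is already clear. D = 12, so t + 36.
- Appendix 3, 3 months = 91 days: at 12 weeks (84 days) the joint still counts; at 16 weeks (112 days) it does not. D = 16, so t + 40.
- Appendix 6, joint active before injection: D never ends.
- SAP Appendix 3.2: D never ends.
- Joint scored only as examined: the injection has no effect and remission comes at Week 24.

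**Results** (first visit completing 24 weeks of inactive disease, 91-day reading for Appendix 3)

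| Injection | Appendix 3 | Appendix 6 | SAP 3.2 | As examined |
|---|---|---|---|---|
| 16 weeks before randomization | Week 24 | never | never | Week 24 |
| 12 weeks before | Week 28 | never | never | Week 24 |
| 8 weeks before | Week 32 | never | never | Week 24 |
| At randomization | Week 40 | never | never | Week 24 |
| Week 4 | Week 44 | never | never | Week 24 |
| Week 8 | Week 48 | never | never | Week 24 |
| Week 12 | Week 52 | never | never | Week 24 |

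For remission the three rules give two outcomes, time-limited or indefinite. Appendix 6 and the SAP agree when the joint was active before injection. They still differ otherwise: the SAP forces Present whatever the earlier status, and forces limited motion, which the parenthesis in Appendix 6 does not mention.

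**Other derived endpoints.** Two joints per 6 months gives at most 2 extra active joints and 2 extra limited-motion joints per 6-month period under the SAP rule. This is an upper bound. A joint already active or limited adds nothing, the sternoclavicular and acromioclavicular joints are not on the limitation-of-motion list (Protocol Section 8.1.1), and JADAS-27 counts 27 joints only (SAP Appendix 3.5).

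**Scale.** The plan is to randomize 54 subjects 1:1 (Protocol Section 10.1.1), so 54 / 2 = 27 per arm. One reclassified child moves an arm's remission proportion by 1 / 27 = 3.7 percentage points. How many children are injected is not stated.

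**The case against.** The strongest objection is that the split classification rests on a document we do not have. The center's manual and SOP are cited but not provided. If the center follows Appendix 6, it and the SAP agree on no remission for a joint that was active before injection. That stands, and the point is worded conditionally for this reason. The conflict between the written rules does not depend on it.

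A second objection is that never in remission is too absolute. It holds only from the injection onward and only with an identifiable site. SAP Table 4 also carries forward the last remission status for completers without saying whether that status is center-confirmed or programmed. Sections 5.2 and 7.1 make the programmed status the likelier reading, but it is not written.

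A reader might go further and infer that the SAP joint rule alters the primary analysis. The documents do not support this. Double-blind flare is taken from the center's real-time assessment (SAP Sections 5.2 and 7.1, Appendix 3.3), so Appendix 3.2 changes no observed flare. SAP Section 2.3.1 censors patients who complete participation after remission, which reads most naturally as disposition and not as programmed status. The primary analysis could be touched only through the protocol's own ambiguity between Appendices 3 and 6, as the center has resolved it.

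It could also be said that Appendix 3 covers background adjustments and Appendix 6 covers rescue. Both limit injections to two joints in 6 months, and no text assigns an injection to one appendix or the other.

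**Conclusion.** The rules conflict and nothing in either document reconciles them. Under the 3-month rule or as-examined scoring, the same child can be a remission completer, censored in the primary analysis, and never inactive in the SAP program after the injection. Under the 3-month rule, completion falls about 36 to 40 weeks after a double-blind injection, depending on whether 3 months is read as 12 weeks or 91 days on 4-weekly visits. Under Appendix 6, with a joint active beforehand, there is no disagreement on remission.

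The consequence is firm for the programmed secondary endpoints and conditional for the classification of completers. The affected child must be injected at a recorded site and then meet every other inactive-disease criterion for 24 weeks, so the group may be very small. Its size cannot be computed from the documents. This should be fixed, but it does not undermine the primary comparison.

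**What to change.** Before unblinding:

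1. Reconcile Protocol Appendix 3, Protocol Appendix 6 and SAP Appendix 3.2 into one rule with one duration. Which rule is right is for the sponsor to decide.
2. Document the rule the coordinating center has actually applied.
3. Require SAP Appendix 3.2 to use that same rule for the derived joint counts, inactive disease, remission, adapted ACR response and JADAS-27.
4. State in SAP Section 2.3.1 that remission censoring follows the center-confirmed status.

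The SAP part is one derivation line and one sentence. Changing the two protocol appendices is a protocol amendment that needs ethics approval (Protocol Section 13.1). With 23 subjects randomized by November 2022 (Protocol Section 10.1.1), past real-time decisions cannot be re-made, so steps 2 and 3 are the part to secure first.

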Appendix 4. Estimated Glomerular Filtration Rate Calculation and Creatinine Clearance Calculation

The Bedside Schwartz²³ GFR equation will be used to estimate glomerular filtration rate (eGFR) from serum creatinine (creatinine method with calibration traceable to IDMS). eGFR will be evaluated at screening to determine if a subject is eligible.

$$\text{eGFR (mL/min/1.73 m}^2\text{)} = 0.413 \times (\text{Ht/Scr})$$

Height (Ht) in cm;

Serum creatinine (Scr) in mg/dL.

In addition, at every study visit a subject's creatinine clearance (CrCl) will be evaluated.

The Modified Schwartz equation will be used to estimate creatinine clearance in participants <12 yrs old.³⁰

$$\text{CrCl (mL/min/1.73 m}^2\text{)} = (\text{K} \times \text{Ht}) / \text{Scr}$$

K (proportionality constant):

Female Child <12 years: K = 0.55

Male Child <12 years: K = 0.70

The Cockcroft-Gault equation will be used to estimate the creatinine clearance for the participants \geq 12 years of age.³⁰

$$\text{CrCl (ml/min)} = [(140 - \text{age}) \times \text{weight in kg}] / [\text{Scr} \times 72] (\times 0.85 \text{ if female})$$

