8.3. Monitoring Hematology and Serum Laboratory Parameters and specific adverse events

8.3.1. Monitoring Criteria

The following laboratory abnormalities require prompt retesting, ideally within 3-5 days:

- Absolute neutrophil count (ANC) $<1.0 \times 10^9/L (<1000/mm^3)$;
- Absolute lymphocyte counts $<0.5 \times 10^9/L (<500/mm^3)$;
- Platelet count $<100 \times 10^9/L (<100,000/mm^3)$;
- Any single hemoglobin value $<8.0 \text{ g/dL}$ or one that drops $\geq 2 \text{ gm/dL}$ below baseline;
- Any single AST and/or ALT elevation $\geq 3 \times$ upper limit of normal (ULN), regardless to total bilirubin. Repeat testing must include the following tests: albumin, creatine kinase (CK), total bilirubin, direct and indirect bilirubin, GGT, PT/INR, and alkaline phosphatase;
- Any single serum creatinine increase $>50\%$ over the average of screening (most recent value prior to baseline) and baseline values OR an absolute increase in serum creatinine $\geq 0.5 \text{ mg/dL} (\geq 44.2 \text{ umol/L})$ over the average of screening (most recent value prior to baseline) and baseline values AND any single CrCl decrease of $>30\%$ over the average of screening (most recent value prior to baseline) and baseline values;
- Increased lipid parameters (total cholesterol, LDL cholesterol, HDL cholesterol, triglycerides) should be monitored and treated according to local guidance (eg, diet and behavior modification, statin therapy).

If the abnormality is confirmed after re-test, follow-up should be discussed with the sponsor and frequency of monitoring increased.

Country specific amendment for EU sites (including UK sites): Study drug will be discontinued temporarily for confirmed absolute neutrophil counts (ANC) levels of 500 - 1000 neutrophils/mm³. The subject will be monitored closely through unscheduled visits and laboratory retesting until ANC is >1000 neutrophils/mm³. Dosing may be resumed when ANC returns to >1000 neutrophils/mm³.

Confirmation should be done based upon central laboratory results, but local laboratory results will be acceptable, particularly if these may be done more promptly.

For additional laboratory abnormalities that require prompt retesting, preferably within 48 hours from awareness of the abnormal results, see [Section 9.7.1](#): Potential Cases of Drug-Induced Liver Injury.

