- Two sequential increases in serum creatinine >50% over the average of screening and baseline values OR an absolute increase in serum creatinine ≥ 0.5 mg/dL (≥ 44.2 umol/L) over the average of screening and baseline values AND a confirmed (two sequential) CrCl decrease of >30% over the average of screening and baseline CrCl values. If the serum creatinine increase and the CrCl decrease have an identifiable and reversible reason (eg, concomitant medication), then an additional retest may be considered after discussion with the Sponsor study clinician or medical monitor. After retest, a decision for the subject to continue in the study will be made after discussion with the Sponsor study clinician or medical monitor.
- Other serious or severe adverse events, in the opinion of the investigator or sponsor. Whenever possible, the investigator should consult with a member of the Pfizer study team before discontinuation of the subject;
- Malignancies, excluding adequately treated or excised basal cell or squamous cell carcinoma of the skin and cervical carcinoma in situ.
- If venous thromboembolism is confirmed, discontinue treatment with tofacitinib.

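### For a child who turns 12 on study, the percent change in creatinine clearance compares two equations in different units, which distorts one leg of the retest and stopping rules

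*Protocol*

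**What the plan says.** Protocol Appendix 4 states that "at every study visit a subject's creatinine clearance (CrCl) will be evaluated". It then gives two equations.

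- Below 12 years: "The Modified Schwartz equation will be used to estimate creatinine clearance in participants <12 yrs old". The formula is K × height / serum creatinine, in mL/min/1.73 m², with "Female Child <12 years: K = 0.55" and "Male Child <12 years: K = 0.70".
- From 12 years: "The Cockcroft-Gault equation will be used to estimate the creatinine clearance for the participants" of 12 or older. The formula is (140 − age) × weight / (72 × serum creatinine), times 0.85 in girls, in mL/min without indexing to body surface area.

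Protocol Section 8.3.2 makes stopping depend on a creatinine rise (two sequential rises above 50%, or an absolute rise of at least 0.5 mg/dL) "AND a confirmed (two sequential) CrCl decrease of >30% over the average of screening and baseline CrCl values". Section 8.3.1 sets the matching retest rule on a single value, and Appendix 7 repeats both rules. SAP Section 6.6 plans a summary of subjects who meet the monitoring and discontinuation criteria.

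Enrolment covers ages 2 to under 18 (Section 4.1), with a target of at least 12 children aged 6 to under 12 (Section 10.1). Open-label treatment lasts 12 to 40 weeks, and the double-blind phase follows. A child can therefore turn 12 on study. Nothing says which equation then applies to the baseline side of the comparison. SAP Section 3.4 fixes age at enrollment for stratification only.

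**The concern.** A percent change is interpretable only if both values are on the same scale. For a child who crosses 12, Appendix 4 read as written puts a height-based, indexed value in the denominator and a weight-based, unindexed value in the numerator. The result mixes any renal change with the difference between the equations at that child's height and weight.

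This matters because the CrCl leg was added, according to the Amendment 4 entry in Appendix 11, to allow for creatinine rising with activity, age and growth. A growing child around 12 is a case that it should handle. Serum creatinine elevation is a safety endpoint, the rule governs retesting and stopping of study drug, and SAP 6.6 will tabulate who met it. A stop in the double-blind phase, other than for clinical remission or study end, also enters the primary analysis as a flare (SAP 2.3.1).

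**Working it through.** The plan gives no CrCl figure to reproduce. The constants below are from Appendix 4. Heights, weights and creatinines are assumptions, because the documents give none.

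**Offset with creatinine unchanged.** Creatinine cancels, so visit CrCl (Cockcroft-Gault, age 12) divided by baseline CrCl (Modified Schwartz) is:

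- boys: (128/72 × W) / (0.70 × H) = 2.540 × W/H
- girls: (0.85 × 128/72 × W) / (0.55 × H) = 2.747 × W/H

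W is weight in kg at the visit and H is height in cm at baseline.

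| Height, weight | Boys | Girls |
|---|---|---|
| 135 cm, 30 kg | -43.6% | -38.9% |
| 142 cm, 35 kg | -37.4% | -32.3% |
| 150 cm, 40 kg | -32.3% | -26.7% |
| 155 cm, 50 kg | -18.1% | -11.4% |
| 155 cm, 70 kg | +14.7% | +24.1% |

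The switch alone exceeds a 30% fall when W/H is below 0.70/2.540 = 0.276 in boys (41.3 kg at 150 cm) or 0.70/2.747 = 0.255 in girls (38.2 kg at 150 cm).

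Units explain only part of this. With Cockcroft-Gault indexed to 1.73 m² (Mosteller body surface area, an assumption), the 150 cm, 40 kg figures become -9.2% and -1.8%. At 150 cm, 65 kg the offset grows, from +10.1% to +15.7% in boys and from +19.1% to +25.2% in girls.

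**When the outcome changes.** Read the rule as (either creatinine leg) AND CrCl. With one equation and constant body size, a 50% creatinine rise gives 1/1.5 − 1 = -33.3%, so the CrCl leg is met without any switch.

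*False trigger.* One equation must leave the CrCl leg unmet while a creatinine leg is met. There are two routes.

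- Growth under Modified Schwartz: (H2/H1)/1.5 ≥ 0.70 requires H2/H1 ≥ 1.05, which is 5% or more in height.
- The absolute-rise leg: s/(s + 0.5) ≥ 0.70 requires baseline creatinine s ≥ 1.17 mg/dL. For example, 1.2 to 1.7 is a 29.4% fall.

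Example: a boy grows from 138 to 152 cm, weighs 42 kg at the visit, and creatinine rises from 0.40 to 0.61 (+53%).

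- Baseline: 0.70 × 138/0.40 = 241.5.
- Schwartz at the visit: 0.70 × 152/0.61 = 174.4, or -27.8% (not met).
- Cockcroft-Gault at the visit: 128 × 42/(72 × 0.61) = 122.4, or -49.3% (met).

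*Missed trigger.* A 50% rise is masked when the offset ratio divided by 1.5 is at least 0.70, so the ratio is at least 1.05. That is W/H ≥ 0.413 in boys (62.0 kg at 150 cm) or ≥ 0.382 in girls (57.3 kg at 150 cm).

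Example: a girl grows from 152 to 155 cm, weighs 62 kg at the visit, and creatinine rises from 0.45 to 0.70 (+56%).

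- Baseline: 0.55 × 152/0.45 = 185.8.
- Schwartz at the visit: 0.55 × 155/0.70 = 121.8, or -34.4% (met).
- Cockcroft-Gault at the visit: 0.85 × 128 × 62/(72 × 0.70) = 133.8, or -28.0% (not met).

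**With one equation on both sides.** At constant body size and creatinine, the birthday effect is 0% under Modified Schwartz and 128/129 − 1 = -0.8% under Cockcroft-Gault.

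**The case against.** A reader might infer from the offsets that a birthday by itself can stop a child's treatment or add a flare to the primary analysis. The documents do not support that. The CrCl leg is joined by AND to a creatinine rise, and the Amendment 4 entry describes the CrCl fall as required in addition to that rise.

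The windows in the examples are narrow. At two decimals, the boy's outcome differs only at creatinine 0.61 and 0.62; at 0.63, Schwartz throughout already gives -30.1%. The girl's trigger is missed only from 0.68 to 0.72; at 0.73 the switched value is -30.9%.

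Nor does CrCl stop tracking renal function after the switch. It still moves inversely with creatinine, with an offset that is modest at some body sizes.

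There are also buffers. Retesting comes first, stopping needs two sequential values, confirmed abnormalities are discussed with the sponsor, and individual data are reviewed throughout. The text does not say whether age at visit or at enrollment governs, so the equation may be fixed in practice.

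All of this limits the consequence. It does not remove the gap: no passage fixes the equation, restates baseline or aligns the units. The extra-retest provision in 8.3.2 is for an identifiable and reversible reason, which does not clearly cover a change of equation, and it does nothing for a missed trigger.

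**Conclusion.** The point holds as a derivation defect of limited reach. Read as written, Appendix 4 and the rules in 8.3.1, 8.3.2 and Appendix 7 give a percent change on mismatched scales for any child who turns 12 on study. The offset is about -44% to +24% over the assumed body sizes, against a 30% threshold. Retest or stopping decisions change only in the limited cases shown in the working.

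Three assumptions carry this. Current age selects the equation at each visit. Baseline is not recomputed. The unbracketed OR/AND means that either creatinine leg must be joined by the CrCl leg. If it instead means that a rise above 50% acts alone, the offset affects only the absolute-rise leg.

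The number of children who turn 12 on study is not given, and those in the initial cohorts were already 12 or older. The documents therefore give no basis for claiming a material effect on the flare count. The case for a change is that the rule should measure what it is meant to measure and that the repair is cheap.

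**What to change.** Reconcile Appendix 4 with Sections 8.3.1, 8.3.2 and Appendix 7, so that the baseline and on-study CrCl entering the percent change are on a comparable basis, in both equation and units, for a child who turns 12. Which equation to use, and the clinical thresholds, are for the sponsor. Aligning the units alone would not be enough, as the heavier-child figures show. Use the same derivation in the SAP 6.6 summary of subjects meeting the criteria.

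The cost is a sentence in Appendix 4, a matching line in the SAP and a change to the CrCl calculation. Height, weight and creatinine are already collected, so no extra sample or visit is needed.
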